### **Concomitant Medications**

Summary on concomitant medications by indication and category both prior to and after tafamadis will be provided using the tafamidis treated set by phenotype at enrollment and overall and prior to tafamidis for untreated set by phenotype at enrollment and overall.

### **Hospitalization**

Summary on the frequency of all hospitalizations, the frequency of ATTR related hospitalizations and the reasons for hospitalizations will be summarized using the tafamidis treated set by phenotype at enrollment and overall, tafamidis untreated set by phenotype at enrollment and overall, CCI [REDACTED]

CCI [REDACTED] and either predominantly cardiac or mixed phenotype at enrollment.

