**Table 2 Data Collection per Visit**

Case Report Form	Eligibility/ Baseline Visit	Return Visits	Retrospective Visits (optional)	Final Visit c
Written informed consent/assent	X	--	--	--
Inclusion/exclusion criteria	X	--	--	--

PFIZER CONFIDENTIAL

Case Report Form	Eligibility/ Baseline Visit	Return Visits	Retrospective Visits (optional)	Final Visit c
Patient demographics date of birth, gender, ethnic origin	X	--	--	--
Clinical trial and compassionate use program participation (log format)	X	X	X	
TTR data genetic test results, tissue biopsy	X	--	--	--
Family history of ATTR amyloidosis	X	--	--	--
Medical history past and current signs, symptoms and medical diagnoses	X	--	--	--
Annual updated medical assessment current signs and symptoms	--	X	--	X
General exam weight/height, vital signs, CCI [REDACTED]	X	X	X	X
Concomitant medications (log format) category, indication, start and stop dates	X	X	X	X
Tafamidis treatments (log format) dose, start and stop dates	X	X	X	
Hospitalizations (log format) admission and discharge dates, reason for hospitalization	--	X	X	X
Transplant history and complications (log format) date(s) of transplant(s), organ(s) transplanted, information on complications	X	X	X	X
Adverse events	X	X	X	X
Laboratory data Hematology, clinical chemistry, urinalysis, including glomerular filtration rate [GFR]	X	X	X	X
CCI [REDACTED]	■	■	■	■
[REDACTED]	■	■	■	■
Nerve conduction studies: Upper Extremity, Lower Extremity				
Renal/bladder ultrasound a residual volume, number and size of kidneys, echogenicity	X	X	X	X

Case Report Form	Eligibility/ Baseline Visit	Return Visits	Retrospective Visits (optional)	Final Visit c
Eye examination a intraocular pressure, vitreous, presence of opacities	X	X	X	X
Body composition a total bone mineral density and content, total lean and fat mass	X	X	X	X
CCI [REDACTED]	■	■		X
Patient death b			X	
Patient discontinuation b			X	
Patient status update b			X	

a Printed assessment worksheets will be available to provide to outside specialists performing assessment(s).

b Data on patient deaths, discontinuations, and status assessments will be collected independent of the visit schedule.

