## 5.2 TAFAMIDIS UNTREATED

The tafamidis untreated set will include the following:

- All available data from patients who have been enrolled in THAOS, signed the informed consent and who have not received tafamidis during the THAOS study.
- All available data before receiving the first dose of tafamidis while in THAOS, for those patients who were not on tafamidis during or after initial enrollment in THAOS but then started receiving tafamidis post enrollment.

Note: Available data after a patient discontinues treatment with tafamidis will be excluded (See Figure 1)

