## 5.3 TAFAMIDIS TREATED

The tafamidis treated set will include the following:

[figure not shown]
- All available data from the enrollment date until final treatment discontinuation of tafamidis or end of follow-up in THAOS (whichever is earlier) for patients who have been enrolled in THAOS, signed the informed consent and who were on tafamidis treatment on or prior to the date of enrollment in THAOS.
- All available data from first dose of tafamidis until final treatment discontinuation of tafamidis or end of follow-up in THAOS (whichever is earlier) for patients who were not on tafamidis at the time of enrollment in THAOS but subsequently initiated treatment with tafamidis.

Note: A patient can be considered part of both the tafamidis untreated and tafamidis treated sets if the patient initiated treatment with tafamidis after beginning participation in THAOS.

The below schematic will help to better understand the patient population to be analysed:

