## **8 STATISTICAL METHODOLOGY AND STATISTICAL ANALYSES**

### **8.1 STATISTICAL METHODS**

The key objectives of the survey are to better understand the natural history of ATTR (hereditary and wild-type forms) and the progression of disease in this patient population. Analysis of clinical outcomes will be conducted on all enrolled patients with available data. Outcomes will be examined separately for the untreated and tafamidis treated sets, as well as for appropriate subgroups within these set. Outcomes will include results of the key clinical, functional and QoL assessments used to define progression of disease.

Data will be summarized descriptively.

Continuous variables will be summarized using descriptive statistics ie, number of non-missing values and number of missing values [ie, n (missing)], mean, median, standard deviation (SD), minimum, maximum and 10th and 90th percentile.

Qualitative variables will be summarized by frequency counts and percentages. Unless otherwise specified, the calculation of proportions will be based on non-missing values.

In case the analysis refers only to certain visits, percentages will be based on the number of patients still present in the study at that visit, unless otherwise specified. Sample size in a subgroup needs to be at least 10 in order to have sufficient data to provide descriptive statistics, listings will be provided for smaller subgroups.

Kaplan-Meier estimates (product-limit estimates) will be presented including the median time with two-sided 95% confidence intervals (CIs), if the number of events are at least 5.

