### **Exposure**

Duration of exposure (in years) among patients receiving tafamidis while enrolled in THAOS will be summarized (excluding time when the patient was part of clinical trial or Compassionate Use/Early Access Program) by starting dose using the tafamidis treated set by phenotype at enrollment and overall, CCI [REDACTED] and either predominantly cardiac or mixed phenotype at enrollment, tafamidis treated set for patients who had severe hepatic impairment at baseline, tafamidis treated set by liver transplantation status (liver transplant prior to first dose of tafamidis/liver transplant after the first dose of tafamidis/no liver transplant).

Additionally the duration of treatment with 20 mg and 61 mg/80 mg will be summarized separately for patients with off label use.

The duration of exposure (in years) will be calculated as:

Sum of all non-missing days when tafamidis was taken (excluding days of other clinical trial/compassionate use participation) / 365.25

Summary of exposure-adjusted Incidence rates (per patient-year) AEs and SAE for Treatment Emergent Adverse events (All causalities) and mortality for tafamidis treated set will be provided.

A separate listing will be provided for duration of exposure listing for patients who switched from 61/80 mg to 20 mg.

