### **Echocardiogram**

For Echocardiogram, summary statistics for the baseline will be provided for:

- Left atrium
- Aortic root
- LV septum
- LV posterior wall

- LV diastolic diameter
- LV systolic diameter
- LV ejection
- RV free wall thickness
- Quantitative LV end systolic volumes
- Quantitative LV end diastolic volumes
- Transmitral E wave peak velocity
- E wave deceleration time
- Transmitral A wave Peak velocity
- Peak tricuspid regurgitation velocity
- Derived peak pulmonary artery systolic pressure
- Septal and Lateral Peak E, A, S
- Stroke volume
- Cardiac output

Also for the following parameters corresponding to Echocardiogram, summaries will be provided at baseline:

- Value abnormalities
- Types of value abnormalities
- Respiratory variation
- Sparkling

Echocardiogram summaries will be performed for the following sets: tafamidis untreated set with predominantly cardiac or mixed phenotype at enrollment, tafamidis treated set with predominantly cardiac or mixed phenotype at enrollment, CCI [REDACTED] and either predominantly cardiac or mixed phenotype at enrollment, tafamidis treated set for patients who switched from predominantly neurologic to mixed phenotype and tafamidis untreated set for patients who switched from predominantly neurologic to mixed phenotype.

*Note: For all the above safety events (Concomitant medications, hospitalization, AE/SAE, Deaths, Laboratory, Vitals and ECG) all events collected till last tafamidis dosing date +28 days will be summarized for the tafamidis treated set and its associated sub-sets.*

CCI [REDACTED]  
[REDACTED]  
[REDACTED]  
[REDACTED]  
[REDACTED]  
[REDACTED]

PFIZER CONFIDENTIAL

CCI [Redacted]

CCI [Redacted]

[Redacted]

[Redacted]

[Redacted]

[Redacted]

[Redacted]

[Redacted]

[Redacted]

[Redacted]

PFIZER CONFIDENTIAL

[Redacted]

CCI [Redacted]

[Redacted]

CCI [Redacted]

[Redacted]

- [Redacted]
- [Redacted]
- [Redacted]
- [Redacted]
- [Redacted]
- [Redacted]
- [Redacted]
- [Redacted]
- [Redacted]
- [Redacted]
- [Redacted]

[Redacted]

CCI [Redacted]

[Redacted]

[Redacted]

CCI [REDACTED]

[REDACTED]  
[REDACTED]  
[REDACTED]

[REDACTED]  
[REDACTED]

[REDACTED]

[REDACTED]  
[REDACTED]  
[REDACTED]

[REDACTED]

[REDACTED]  
[REDACTED]  
[REDACTED]

[REDACTED]

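### Hospitalizations are summarised only as frequencies, with no person-time denominator, although observation windows differ by construction between and within the treated and untreated sets

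*SAP*

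**What the plan says.** SAP 8.2.6, Hospitalization, gives the measure: "Summary on the frequency of all hospitalizations, the frequency of ATTR related hospitalizations and the reasons for hospitalizations will be summarized". The groups are the "tafamidis treated set by phenotype at enrollment and overall, tafamidis untreated set by phenotype at enrollment and overall", plus a partly redacted subgroup with predominantly cardiac or mixed phenotype. The word frequency is not defined there. The nearest general rule is in SAP 8.1: "Qualitative variables will be summarized by frequency counts and percentages".

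The windows are set elsewhere in the SAP:

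- **Untreated set (5.2).** Patients who never receive tafamidis in THAOS contribute all their data. Those who start it after enrollment contribute "All available data before receiving the first dose of tafamidis while in THAOS".
- **Treated set (5.3).** Patients who start after enrollment contribute "All available data from first dose of tafamidis until final treatment discontinuation of tafamidis or end of follow-up in THAOS (whichever is earlier"). Those already on tafamidis at enrollment contribute from the enrollment date.
- **Extension (note at the end of the Echocardiogram subsection, which names hospitalization).** "all events collected till last tafamidis dosing date +28 days will be summarized for the tafamidis treated set".
- **Exclusions (2.1, Assessments).** Data from periods in other trials or in compassionate-use programmes are left out.

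Person-time rates are planned, but only in the Exposure subsection: "Summary of exposure-adjusted Incidence rates (per patient-year) AEs and SAE for Treatment Emergent Adverse events", together with mortality, for the treated set. The Amendment 2 table in SAP section 1 justifies them by noting that exposure may differ between dose groups. Hospitalization is not in that list. The hospitalization log holds "admission and discharge dates, reason for hospitalization" (SAP Table 2).

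**The concern.** A count of admissions, or a percentage of patients with at least one, rises with time observed even when the underlying rate does not change. The SAP accepts this for adverse events and mortality and moves to per-patient-year rates there. It does not do so for hospitalization, although that summary covers both sets and every phenotype.

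The stake is descriptive. Natural history and disease progression are stated objectives (protocol section 8, SAP 2.2). Protocol 7.2 says that event-of-interest data in untreated participants should give context to safety events in treated participants. The two sets of tables will therefore be read together. Protocol 7.1 also names cardiovascular-related hospitalization in the US cardiomyopathy indication, so readers will look at this table. Deaths are reported as n (%) too, but Kaplan-Meier estimates accompany them; hospitalization has no equivalent companion.

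**Working it through.** The plan states no hospitalization rate, follow-up length or sample size, so there is no planned figure to reproduce. The check has three parts.

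**1. Windows, set by set (SAP 5.2, 5.3 and the +28-day note)**

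| Patients | Start | End for counting hospitalizations |
|---|---|---|
| Untreated, never on tafamidis in THAOS | enrollment | end of follow-up |
| Untreated, later starters | enrollment | first dose |
| Treated, started after enrollment | first dose | last dose + 28 days, or end of follow-up |
| Treated, already on tafamidis at enrollment | enrollment | last dose + 28 days, or end of follow-up |

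Nothing makes these lengths equal, and the untreated set mixes truncated with untruncated patients. The extension itself is small: 28 / 365.25 = 0.077 years. At an assumed 0.3 admissions per patient-year that adds 0.3 × 0.077 = 0.023 admissions per patient. It matters mainly because numerator and denominator must agree.

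**2. Ceiling on treated time by indication**

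Inputs are the approval dates in protocol 7.1 and the planned end of data collection, 16 June 2023, in protocol section 6. Where only a month is given, its first day is used.

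- Polyneuropathy, EU, 16 November 2011: 4,230 days / 365.25 = 11.6 years.
- Cardiomyopathy, Japan, March 2019: 1,568 / 365.25 = 4.3 years.
- Cardiomyopathy, EU, February 2020: 1,231 / 365.25 = 3.4 years.

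These are maxima for on-label commercial use, not averages, and indication is not identical to the SAP's phenotype. They show that treated time *can* differ widely between phenotypes, not that it does.

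**3. Effect of unequal follow-up at equal rates**

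Assumptions: a constant Poisson rate λ of 0.1 to 0.6 per patient-year, and follow-up t of 2 or 4 years. None of these values comes from the documents.

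- Admissions per 100 patients = 100 × λ × t
- Share with at least one admission = 1 − exp(−λt)
- Rate per 100 patient-years = 100 × λ, which does not depend on t

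| λ | Admissions per 100, 2 y | 4 y | At least one, 2 y | 4 y | Per 100 patient-years |
|---|---|---|---|---|---|
| 0.1 | 20 | 40 | 18.1% | 33.0% | 10 in both |
| 0.3 | 60 | 120 | 45.1% | 69.9% | 30 in both |
| 0.6 | 120 | 240 | 69.9% | 90.9% | 60 in both |

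The order can also reverse. At 0.3 over 2 years there are 100 × 0.3 × 2 = 60 admissions per 100 patients, and 1 − exp(−0.6) = 45.1% have at least one. At a lower rate of 0.2 over 4 years there are 100 × 0.2 × 4 = 80, and 1 − exp(−0.8) = 55.1%. The group with the lower rate shows the higher frequency.

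**The case against.** The strongest case against is that nothing here is compared. SAP section 4 states no hypotheses and makes every analysis descriptive, and 8.1 has outcomes examined separately in the two sets. The only comparative objective concerns progression and survival with and without liver transplant. Hospitalization is not among the safety endpoints named in 6.2. This stands as a limit: no test or decision rule is affected. It does not rescue the summary, because a descriptive figure should still be interpretable within its own set and phenotype.

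Other points have partial force:

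- Follow-up time is tabulated by set and phenotype (8.2.2), so a reader could make a crude adjustment. The SAP does not plan one.
- An admission for a medical event is an SAE (protocol 11.4.3 and 11.5), so in the treated set such admissions already enter the per-patient-year SAE rate. The untreated set has no counterpart.
- Frequency is undefined and parts of the section are redacted. That the table will hold unadjusted counts and percentages is an inference from 8.1 and from the contrast with the Exposure subsection.
- A crude rate removes the duration effect fully only if the hazard is constant, which is doubtful in a progressive disease. Assessments are recommended rather than required, so ascertainment may differ too.

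A reader might infer that untreated follow-up always stops at tafamidis start. That is true only of later starters. A reader might also infer that a particular set or phenotype will look worse. The documents do not support that, since they do not say which group is followed longer. Nor do they show that the frequencies mainly reflect length of observation or say nothing about natural history. Counts with reasons and ATTR-relatedness still describe burden within a group.

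**Conclusion.** The point holds as a reporting weakness in a descriptive plan. As written, the hospitalization frequencies are confounded by length of observation, within each set and between sets and phenotypes. The windows differ by definition, and the SAP already uses the remedy for other events.

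Size and direction cannot be determined from the documents. Under assumed constant, equal rates of 0.1 to 0.6 per patient-year, 4 rather than 2 years of follow-up moves the share with at least one admission by about 15 to 25 percentage points (33.0 − 18.1 = 14.9; 69.9 − 45.1 = 24.8; 90.9 − 69.9 = 21.0). If actual follow-up proves similar across groups, the distortion between them will be small. The conclusion rests on reading frequency as counts and percentages and on no hospitalization rate standing in the redacted text.

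**What to change.** Add to SAP 8.2.6, Hospitalization, for each set and phenotype, beside n (%):

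- total patient-years at risk;
- crude admissions per patient-year, all-cause and ATTR-related separately, with 95% CI that allow for repeat admissions within a patient (for example a robust variance or a bootstrap by patient).

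Define time at risk so that it matches the counting window. For the untreated set, run from enrollment to first dose for later starters and to end of follow-up otherwise. For the treated set, run from first dose or enrollment and include the 28 days after last dose where they fall within follow-up. Remove trial and compassionate-use time from numerator and denominator alike. The formula in the Exposure subsection should not be reused unchanged: it sums dosing days only, so it omits treatment gaps and the 28 days while admissions in those periods are counted. State what frequency means (admissions, patients, or both).

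No negative binomial or other regression model is needed in a descriptive plan, and no new data are required. The cost is a short definition of person-time and a little programming, mostly to derive untreated time. The rate removes the person-time artefact. It does not remove confounding between sets, and a footnote should say so.

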### Adverse Events & Serious Adverse Events

All adverse events will be coded according to the latest Medical Dictionary for Regulatory Activities (MedDRA) version at the time of analysis.

Adverse events (all causality and treatment-related) will be summarized by severity and starting dose using the tafamidis treated set by phenotype at enrollment and overall, CCI [REDACTED] and either predominantly cardiac or mixed phenotype at enrollment, tafamidis treated set for patients who had severe hepatic impairment at baseline, tafamidis treated set by liver transplantation status (liver transplant prior to first dose of tafamidis/liver transplant after the first dose of tafamidis/no liver transplant).

Separate summaries will be provided for all AEs, treatment related AEs, all SAEs, treatment related SAEs, AEs leading to dose reduction, AEs leading to withdrawal of tafamidis (temporarily or permanently, or delayed) and AEs leading to tafamidis dose interruptions.

Listings will be provided for adverse events corresponding to all enrolled patients and for patients with off-label usage of tafamidis. A separate listing of SAEs will also be provided for tafamidis treated set.

The following AE summary tables will be provided corresponding to some of the important potential risks using the tafamidis treated set.

- For **hepatotoxicity** using the search criteria: MedDRA SMQ (Standardized MedDRA Query) [Broad and narrow] Drug related hepatic disorders – comprehensive search. The derivations and conventions related to the search criteria will follow the programming specifications done in the Periodic Safety Update Report (PSUR) 12 for tafamidis.
- For **reproductive and developmental toxicity and lactation**:
  - MedDRA SMQ (Broad and narrow): Congenital, familial and genetic disorders; Foetal disorders; Neonatal disorders, Neonatal exposures via breast milk.
  - MedDRA Preferred terms (PTs): Exposure during pregnancy, Exposure via father, Foetal exposure during delivery, Foetal exposure during pregnancy, Foetal exposure timing unspecified, Maternal exposure before pregnancy, Maternal exposure during delivery, Maternal exposure during pregnancy, Maternal exposure timing unspecified, Drug exposure before

- pregnancy, Exposure via breastmilk, Maternal drug affecting foetus, Maternal exposure during breastfeeding
- The derivations and conventions related to the search criteria will follow the programming specifications done in the PSUR 12 for tafamidis.
  - For **changes in thyroid function**, using the search criteria: MedDRA SMQ (Broad and narrow): Thyroid dysfunction. The derivations and conventions related to the search criteria will follow the programming specifications done in the PSUR 12 for tafamidis.
  - For **off-label use**, MedDRA PTs: product use in unapproved indication, Product use issue, Intentional product use issue, Drug effective for unapproved indication, Drug ineffective for unapproved indication

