8.2.5, 8.2.7	
CCI [REDACTED]
 
[REDACTED]
 
[REDACTED]
 
[REDACTED] see section 6.1.
 
Updated derivation of duration of exposure to tafamidis.
	
Descriptive nature of the study limits efficacy analysis.
 
Since a subject may participate in other clinical/compassionate trials while being enrolled in THAOS, the period of such trials needs to be excluded from the safety analysis, including exposure, hence an updated derivation for duration of exposure has been used.

CCI [REDACTED]	[REDACTED]	[REDACTED]
8.2.6	Update on survival analysis.	Moved survival analysis section to safety section in order to be consistent with section 6.2. Kaplan-Meier estimates will be provided if the number of events are at least 5.
8.2.6 (previous section 8.2.7)	Summary on dose increase/decrease/stop to be removed due to limitation in CRF.	The CRF only collects limited information for stopping tafamidis dose which cannot be attributed

		directly to whether dose was increased/decreased.
	Concomitant medications both prior to tafamidis and after tafamidis for treated patients and prior to tafamidis for untreated patients.	Added additional clarification to SAP.
	Added text to safety section: “exposure-adjusted incidence rate”. Summary of incidence rates (per patient-year) for AEs and SAE Treatment Emergent Adverse events (All causalities) and mortality for tafamidis treated set” will be provided.	Duration of exposure can be different in the low, high and switched dose groups.
	Hy’s law table to be excluded.	Hy’s law requires conditions to check whether the lab value is beyond ULN, however THAOS database does not collect records/data on the ULN values for lab parameters.
	Provide duration of exposure listing for patients who switched from 61/80 mg to 20 mg.	Sample is expected to be too small to allow for descriptive statistics. Listing will be provided.
	For all safety events (Concomitant medications, hospitalization, AE/SAE, Deaths, Laboratory, Vitals and ECG) all events collected till last tafamidis dosing date +28 days will be summarized for the tafamidis treated set and its associated sub-sets.	Added additional clarification to SAP.
CCI		

		CCI [REDACTED]
[REDACTED]	[REDACTED]	[REDACTED]
[REDACTED]	[REDACTED]	[REDACTED]
[REDACTED]	[REDACTED]	[REDACTED]

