### Hematology and Chemistry

Change from baseline by yearly intervals of the hematology and biochemistry laboratory parameters will be provided using the tafamidis treated set by starting dose.

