8.2.8 Summary of Analyses

Data	All enrolled	Untreated overall & by phenotype	Untreated predominantly neurologic/mixed	Untreated predominantly cardiac/mixed	Treated Overall and by phenotype	Treated predominantly neurologic/mixed	Treated predominantly cardiac/mixed	Treated by starting dose	[REDACTED]	[REDACTED]	Treated severe hepatic impaired at baseline	Patients not on tafamidis at the time of enrollment with a liver transplant prior to enrollment on THAOS	Patients not on tafamidis at the time of enrollment with a liver transplant after enrollment on THAOS	Patients not on tafamidis at the time of enrollment with no liver transplant	Treated with liver transplant prior to first dose of tafamidis in the study	Treated with liver transplant after first dose of tafamidis in the study	Treated with no liver transplant either prior to first dose of after first of tafamidis in the study	Treated with off-label usage	Untreated predominantly neurologic who become mixed	Untreated predominantly cardiac who become mixed	Treated predominantly neurologic who become mixed	Treated predominantly cardiac who become mixed
Disposition	x	x			x																	
Demography	x	x			x																	
Disease Characteristics	x	x			x																	
Misdiagnoses	x	x			x																	
Ongoing symptoms by A.T.T.R		x			x				x													
relatedness (definite/possibly related/unrelated)																						
Past symptoms by A.T.T.R		x			x																	
relatedness (definite/possibly related/unrelated)																						
New symptoms by A.T.T.R		x			x																	

PFIZER CONFIDENTIAL

CCI				x			x		x			x							x			x	
				x			x		x														
			x			x						x	x	x							x		x
Survival		x			x					x	x	x	x	x	x	x	x						
Exposure to Tafamidis					x			x		x	x				x	x	x						
Concomitant medications		x			x																		
Hospitalizations		x			x					x													
AE/SAE					x			x		x	x				x	x	x	x					
Death	x	x			x					x	x	x	x	x	x	x	x						
Labs – baseline and change from baseline		x			x			x															
Hy's Law					x			x															

Blood pressure – baseline and change from baseline	x	x			x															
ECG				x			x			x								x		x
ECHO				x			x			x								x		x
CCI		x			x															
[REDACTED]			x			x														
[REDACTED]			x			x														
[REDACTED]			x			x														
[REDACTED]				x			x		x									x		x
[REDACTED]				x			x													
Transplant		x			x															
[REDACTED]		x			x															

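### Starting dose is the only dose split in the safety tables, so events at 61/80 mg in patients who began on 20 mg count under 20 mg and distort the dose columns

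*SAP*

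**What the plan says.** SAP 8.2.6 (Adverse Events & Serious Adverse Events) has AEs that "will be summarized by severity and starting dose using the tafamidis treated set by phenotype at enrollment and overall". Changes in haematology and chemistry "will be provided using the tafamidis treated set by starting dose", and the Blood Pressure paragraph uses the same grouping for treated patients. In the grid in SAP 8.2.8 the only legible column that splits treated patients by dose is "Treated by starting dose"; two neighbouring column heads are redacted.

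Other provisions touch on dose:

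- The Exposure paragraph of 8.2.6 plans a "Summary of exposure-adjusted Incidence rates (per patient-year) AEs and SAE for Treatment Emergent Adverse events (All causalities) and mortality for tafamidis treated set", with no dose split stated. Its own duration summaries are by starting dose.
- For off-label patients only, the Exposure paragraph summarises time on 20 mg and time on 61/80 mg separately.
- For one direction of switching there is a listing of exposure: "A separate listing will be provided for duration of exposure listing for patients who switched from 61/80 mg to 20 mg".
- SAP 5.4 defines off-label use as not being predominantly cardiac or mixed at the first 80/61 mg dose. That subgroup has its own AE listing in 8.2.6 and an AE/SAE entry in 8.2.8.
- The Amendment 2 table in SAP section 1 justifies the exposure-adjusted rates thus: "Duration of exposure can be different in the low, high and switched dose groups".
- SAP Table 2 shows that the tafamidis treatment log collects "dose, start and stop dates".

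**The concern.** The plan expects some patients to take both doses. SAP 8.2 gives off-label patients a baseline just before their first 80/61 mg dose, and the two-dose duration summary would have little purpose if nobody changed dose. Yet each treated patient's events stay in the column of the first dose, however long the second dose is taken.

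The calendar makes movement from 20 mg to 61/80 mg possible on a real scale. Protocol 7.1 dates EU approval of tafamidis meglumine for polyneuropathy to November 2011, and Protocol 7.3 identifies the product as a 20 mg capsule. Protocol 7.1 dates the cardiomyopathy approvals at 61 or 80 mg to March 2019 (Japan), May 2019 (US) and February 2020 (EU). Protocol section 6 ends data collection in June 2023.

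The study is a post-authorisation safety commitment. A reader of its report will compare the dose columns because the plan chose to print them. If high-dose events sit in the low-dose column, that reading is unsafe in a way the table does not disclose.

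**Working it through.** The documents state no AE rate, dose contrast or switching share, so there is no planned figure to reproduce. The check is an illustration.

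**Who is covered by the existing outputs**

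| Patient | Dose-specific output beyond starting dose |
|---|---|
| 20 mg to 61/80 mg, off-label by phenotype at first 61/80 mg dose | Duration on each dose; AE listing; AE/SAE subgroup entry |
| 20 mg to 61/80 mg, predominantly cardiac or mixed at that time | None |
| 61/80 mg to 20 mg | Exposure listing only |

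Even in the first row, the text does not say that events are separated by the dose at onset.

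**How large the switched share could be for one patient.** For EU dates, November 2011 to February 2020 is 99 months and February 2020 to June 2023 is 40 months. A patient on 20 mg from the first date who moved at the second would have 40/139 = 29% of exposure at the higher dose. A hypothetical January 2019 starter who moved at the same time would have 40/(13 + 40) = 75%. These are individual bounds. The group average cannot be derived from the documents.

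**Per-patient-year rates, constant hazards.** Let k be the true rate ratio (61/80 mg to 20 mg) and s the share of 20 mg starters' exposure at 61/80 mg. Assume that 61/80 mg starters stay on that dose. Then the ratio seen by starting dose is k / [(1 − s) + s·k].

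| s (assumed) | k = 1.5 | k = 2.0 |
|---|---|---|
| 25% | 1.5/1.125 = 1.33 | 2.0/1.25 = 1.60 |
| 50% | 1.5/1.25 = 1.20 | 2.0/1.50 = 1.33 |
| 75% | 1.5/1.375 = 1.09 | 2.0/1.75 = 1.14 |

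The pull works from below as well: k = 0.67 with s = 50% gives 0.67/0.835 = 0.80. If 5% of the 61/80 mg starters' time is at 20 mg, the k = 1.5, s = 50% figure becomes (0.95 × 1.5 + 0.05)/1.25 = 1.18, so the reverse switch adds little. Assigning events and time to the dose at onset returns k itself in this model.

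**Crude percentages.** The starting-dose AE tables are not stated to be rates. Assume 0.10 events per patient-year at 20 mg, k = 1.5, and percentage with an event = 1 − exp(−cumulative hazard). A switcher has 3 years at 20 mg and 2 years at 61/80 mg: 1 − exp(−0.3 − 0.3) = 45.1%. A non-switcher with 5 years at 20 mg has 1 − exp(−0.5) = 39.3%.

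| Follow-up of 61/80 mg starters | 61/80 mg column | 20 mg column, share of patients switching | Difference (points) |
|---|---|---|---|
| 5 years (equal) | 1 − exp(−0.75) = 52.8% | 39.3% (none) | +13.4 |
| 5 years | 52.8% | 41.1% (30%) | +11.7 |
| 5 years | 52.8% | 42.8% (60%) | +10.0 |
| 2 years (unequal) | 1 − exp(−0.30) = 25.9% | 39.3% (none) | −13.4 |
| 2 years | 25.9% | 41.1% (30%) | −15.2 |

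Differences are taken before rounding. In the last two rows the sign is already reversed without any switching, so unequal follow-up causes the reversal and switching deepens it. Both faults call for patient-years by dose.

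**The case against.** The case for leaving the plan alone has real content. Starting dose is fixed at baseline, places each patient once, and is a legitimate grouping. SAP section 4 states no hypotheses and makes everything descriptive, and no objective compares doses. Many neurologic-phenotype switchers are visible through the off-label outputs. The switcher listing that the plan does provide concerns the opposite direction, and the Amendment 2 table expects that group to be too small for statistics. The same table also says that the CRF holds limited information on why a dose was stopped.

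Most of this limits the point without removing it. In a descriptive study the table is the result, so a misassigned event is still misassigned. The off-label route leaves out patients who are predominantly cardiac or mixed when they move. The CRF limitation concerns reasons for stopping; the dose and its dates are collected.

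Three stronger readings are tempting and the documents do not support them:

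- A reader might infer that any dose difference is necessarily diluted. That holds for per-patient-year rates under constant hazards. The AE tables are not stated to be rates, and crude percentages can go the other way.
- A reader might infer that higher-dose safety was a main reason for extending the registry to cardiomyopathy. Protocol 7.3 speaks of important potential risks and missing information, the stated gap in Protocol 7.2 and section 8 is NYHA Class IV, and dose is not a listed concern in Protocol Table 1 or in the legible part of SAP Table 1.
- A reader might treat the Amendment 2 wording as an inconsistency. A change log is not operative text. It shows only that a switched group was contemplated.

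**Conclusion.** The point stands as a weakness that should be corrected in a descriptive safety output. Events at 61/80 mg in 20 mg starters are counted under 20 mg, and no existing output corrects this for patients who are predominantly cardiac or mixed when they change. No legible operative section defines or tabulates a switched-dose group.

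The size is unknown. The attenuation figures above rest on assumed switching shares, assumed rate ratios and constant hazards; the crude percentages also rest on an assumed 20 mg rate and assumed follow-up. They show that the distortion could matter, not that it will. Nor would assignment by dose at onset yield a causal dose effect: in Protocol 7.1 and 7.3 the 20 mg product is tied to polyneuropathy and 61/80 mg to cardiomyopathy, so dose tracks indication.

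**What to change.** Keep the starting-dose tables. In SAP 8.2.6 add exposure-adjusted AE and SAE rates by dose at onset:

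- Split each patient's time at every dose change, using the dose and dates in the tafamidis log, and use patient-years on each dose as the denominator.
- Assign an event to the dose being taken at onset.
- Apply the 28-day tail only after a dose period that is not followed directly by another. If there is a gap, end the tail when the next dose starts. The existing rule at the end of 8.2.6 refers to the last tafamidis dose and does not settle this. A tail after every dose period would send early events after a direct switch back to the previous dose.
- Define the low, high and switched groups, and report the number of patients and patient-years in each.
- Show the rates by phenotype as well as overall.

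The cost is one further set of AE/SAE tables and no new data collection. Switchers will appear in both columns, and time on a later dose comes from patients who tolerated the first; with the link between dose and indication, these need a footnote. Imputed dates add some noise: under SAP section 7 a missing tafamidis start day becomes the 15th, while other missing days become the 1st, so a direct switch with both days missing in one month would look like a 14-day gap. The derivation should say how this is handled. The laboratory and blood pressure tables can stay as they are, with a footnote that their columns follow starting dose.
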